
C.7 MEG Correlated with PCS Scores and Neuropsychological Scores in mTBI

MEG slow-wave correlates with PCS score in mTBI: Voxel-wise correlational analyses of MEG slow-wave measures and PCS were performed in the blast and non-blast mTBI groups described in C.2. Significant positive correlations were found between MEG source magnitude and PCS scores (Fig. 8, $r>0.55$) [1]. In the blast mTBI group, personality symptoms (e.g., social problems) correlated with MEG slow-waves in bilateral OFC and medial PFC; trouble concentrating and affective lability both correlated with slow-waves in left OFC; blurred vision/visual difficulties correlated with slow-waves in right fusiform gyrus. In the nonblast mTBI group, depression symptoms correlated with slowwaves in ACC. In combined blast and non-blast mTBI groups, only MEG source magnitude from right OFC correlated with trouble concentrating (not shown). The threshold of the voxel-wise analyses was at $q=0.05$ by FDR [85]. These results support Hypothesis 6. MEG slow-wave correlates with neuropsychological scores in 31 mTBI patients: Fig. 9 shows brain regions with negative correlations ($|r| > .45$) between rs-MEG slowwave magnitude and performance on DKEFS Color Word Interference test. Specifically, poorer inhibitory control was associated with higher rs-MEG slow-wave magnitude in the right dIPFC, bilateral supramarginal gyri, ACC, right hippocampus, and left inferior temporal lobe. These results also support Hypothesis 6. **Figure 8 and 9**

- See attached document.

C.8. Preliminary Data for Nexalin

The pulse-based tES (as administered by the Nexalin apparatus) is a way to alter brain functions with low intensity electrical current undetectable by the participants. . A prior randomized, controlled trial compared antidepressant medication with Sham TES, Placebo with Nexalin at a lower dose, and Placebo medication with Nexalin at a higher dose. All three conditions showed remission of depressed mood by the end of treatment and maintenance of remission status following 12 weeks of follow-up. Thus, the effect sizes for Nexalin treatment were comparable to antidepressant medication. It should also be noted that the Nexalin device has undergone extensive safety analysis indicating that the device is safe for its intended use. Additionally, the classification of the device places it into a nonsignificant risk (low risk device) category. A review of Phase III Pivotal Clinical Trials (with a follow up period of one year) demonstrates that Nexalin TES Therapy does not result in any significant adverse events or side effects. In fact, there was no significant difference between reported events in the placebo group and reported events in the active treatment group.

Section 9 - Design and Methods

9) Describe the research design and the procedures to be used to accomplish the specific aims of the project. Provide a precise description of the planned data collection (include what systems or databases will be used/accessed to gather data), analysis and interpretation. For chart review studies, include the timeframe of collection. Address sample size, inclusion of women and minorities. Define in clear terms exactly what will be done to the human subjects.

D. RESEARCH DESIGN AND METHODS

D.1 Human Subject Recruitment, Clinical Symptoms, Neuropsychological Exams

D.1.1. Human subject recruitment and flow chart:

This study will assess traumatic brain injury among Veterans using either blast-related and non-blast related criteria. The research results will be generalizable to the Veteran population who also incur head injuries from sports, falls, or motor vehicle crashes.

We propose to study a total of 175 subjects in three groups. Two groups contain OEF/OIF/OND Veterans (age 18-60) diagnosed with chronic mTBI with persistent PCS (majority due to blast). Participants in these two groups will be matched on age, gender, education, combat exposure, symptom chronicity, and socioeconomic status. Group 1 (mTBI-IASIS group, N=50) contains mTBI Veterans to be blindly assigned to a 6-weeks IASIS treatment with two sessions per week. Group 2 (mTBI sham group, N=50) contains mTBI Veterans to be blindly assigned to a sham treatment for 6 weeks with also two sessions per week. Veterans with mTBI in both Groups 1 and 2 must currently have persistent PCS at least 6 months post injury (i.e., the most recent injury). In addition, PTSD symptoms will be assessed and matched in symptom severity and diagnostic category in the two mTBI groups. Group 3 (control group, N=75): age-, gender-, education-, combat exposure-, and socioeconomically-matched HC Veterans.

The above table and Fig. 10 shows the study flow chart with 16 visits. After consent, Visit 1 for all three groups will include baseline neuropsychological (NP) and mental health assessment (MHA). Then, baseline rs- MEG and MRI scans will be performed in Visit 2 for all participants. The rs-MEG data from the HC group will be used to establish a normative HC database. Next, a re-test rs-MEG exam will be performed in a subset of HC participants (N=25, green dashed line) at Visit

3 in order to confirm the test-retest-reliability of the normative database. In contrast, at Visit 3 the mTBI participants in IASIS and sham groups will undergo a pre-session MEG, the first IASIS /Sham treatment session (S1), and a post-session MEG exam. The pre-session MEG in Visit 3 can be used as a re-test exam with respect to the Visit 2 baseline MEG for analyzing test-retest-reliability in the mTBI groups. In addition, the same pre-session MEG exam in Visit 3 will be compared with Visit 3 post-session MEG to assess possible potentiation of slow-waves due to the IASIS session (or lack of potentiation in the sham session). Next, the mTBI participants continue their IASIS/Sham treatment sessions (S2-S6) in visits 4-8. During the mid-treatment Visit 9, another pair of pre- and post-session MEG exams and NP will be performed. The mTBI participants will continue treatment sessions (S8-S11) in Visits 10-13. During the final treatment Visit 14, the third pair of pre- and post-session MEG exams will be performed. One week after the participants finish their final IASIS/Sham treatment session (S12), a one-week follow-up MEG and NP exams will be conducted during Visit 15. Finally, a subset of IASIS group (N=25) will be tested one month after the final treatment for a one-month follow-up MEG. To reduce drop-out rate, participants initially in the mTBI-sham group will also be offered the real IASIS treatment, but no MEG or behavioral data will be collected for that treatment. **Figure 10 - See attached document.** If, after IASIS treatment is complete and participants in the mTBI group may have remaining PCS, additional Nexalin treatment will be offered.

D.1.2. Exclusion criteria for study participations include: 1) history of other neurological, developmental, or psychiatric disorders (based on the DSM-5 (MINI-7) [86] structured interview), e.g., brain tumor, stroke, epilepsy, Alzheimer's disease, schizophrenia, bipolar disorder, ADHD, or other chronic neurovascular diseases such as hypertension and diabetes; 2) substance or alcohol use disorders according to DSM-5 [87] criteria within the six months prior to the study; 3) history of metabolic or other diseases known to affect the central nervous system (see [88] for similar criteria); 4) Metal objects (e.g., shrapnel or metal fragments) that fail MRI screening, or extensive metal dental hardware (e.g., braces and large metal dentures; fillings are acceptable) or other metal objects in the head, neck, or face areas that cause non-removable artifacts in the MEG data; 5)

Potential subjects will be administered the Beck Depression Inventory (BDI-II) to evaluate level of depressive symptoms, and suicidal ideation; any participant who reports a "2" or "3" on the BDI-II: item 9 (suicidal thoughts or wishes) will also be excluded. However, depression following mTBI or traumatic event of PTSD is common [89]; therefore, in two mTBI groups, we will include and match patients with depression symptoms reported after their injury/event, and will co-vary BDI-II score in data analyses.

D.1.3. Inclusion for the mTBI groups: All symptomatic mTBI patients will be evaluated in a clinical interview to document the nature of the injuries and ongoing PCS. The diagnosis of mTBI patients is based on standard VA/DOD diagnostic criteria. Inclusion in the mTBI patient group requires a TBI that meets the following criteria: 1) a loss of consciousness (LOC) < 30 minutes or transient confusion, disorientation, or impaired consciousness immediately after the trauma; 2) post-traumatic amnesia (PTA) < 24 hours; 3) an initial Glasgow Coma Scale (GCS) [90] between 13-15 (if available). Since the GCS assessment is often not available in theater, Veterans with missing GCS, but who meet other inclusion criteria will also be recruited. Each patient must have at least 3 items of persistent PCS (see below) at the beginning of the study.

D.1.4. Inclusion of HC group: Participants that qualify as HCs will be age, education, combat exposure, and socioeconomically matched to the mTBI groups. In addition to exclusion criteria listed above, HC subjects must not have been diagnosed with head injury, affective disorder, or PTSD (CAPS-5 < 8) throughout life.

D.1.5. Assessing persistent PCS scores in mTBI: Ongoing PCS in mTBI will be assessed utilizing the Neurobehavioral Symptom Inventory (NSI) [91] and Rivermead Post-concussion Symptom Questionnaire (RPQ) [20]. NSI is a PCS questionnaire widely used in Veterans [91]. The NSI was devised to gauge the severity of PCS and track symptoms over time, and is a 22 item self-report questionnaire that assesses severity of cognitive, somatic, and emotional symptoms. The severity of PCS is measured using a Likert scale ranging from 0 (not experiencing) to 4 (a very severe problem), thus, NSI allows for a correlational analysis between symptom severity and MEG findings. While the NSI is able to track PCS symptoms over the last 2 weeks, we will also assess the PCS using the RPQ [20], a 16-category questionnaire that addresses PCS symptoms over the last 24 hours. As we will be performing multiple IASIS sessions, this 24 hour scale is required. For Veterans with blast mTBI, we will also collect information about secondary and tertiary injuries. At baseline, we will assess combat exposure using the Combat and Post-battle Experiences Scales of the

Deployed Risk and Resilience Inventory 2 (DRRI-2) [6], which takes into account the amount level of combat and post-battle exposures, and this coupled with a clinical interview that will detail the amount of times each participant has been exposed to a possible subconcussive blast. In patients with multiple mTBIs, a history of the most recent and all prior mTBIs (life-long) will also be documented for analyzing the effects of repetitive mTBI on MEG slow-wave source imaging. In patients with multiple TBIs, both old and new injuries may contribute to the generation of abnormal MEG slow-waves. Lifetime history of TBI will be assessed using the Ohio State University Traumatic Brain injury Identification method (OSU TBI-ID) [19]. Since sleep is

often disrupted in mTBI, the Pittsburgh Sleep Quality Index (PSQI) [17] will be given to assess for 7 different components of sleep: subjective sleep quality, sleep latency, sleep duration, habitual sleep efficiency, sleep disturbances, use of sleep medications and daytime dysfunction over the last month. The McGill Pain Questionnaire (MPQ) [18] will evaluate the level of current pain, pain changes over time, and strength of pain, since pain is frequently co-morbid with mTBI. In addition, the order of mTBI to PTSD will be collected.

D.1.6. Assessing mental health PTSD symptoms: At Visit 1, participants in all three groups will be evaluated by a psychologist or research associate under the supervision of Co-I, [name], using a structured clinical interview, the Mini- International Neuropsychiatric Interview (MINI-7) [86] to rule in/out mental health disorders, and the Clinician- Administered PTSD Scale (CAPS-5) [7] for DSM-5 [87]. The CAPS-5 is a standard semi-structured interview used to assess PTSD diagnosis and severity. As part of a structured interview, the primary traumatic event is elicited and will be used as the basis of assessing PTSD symptoms. The CAPS-5 total symptom severity score is calculated by summing severity scores for the DSM-5 PTSD symptoms that are assessed with this 30 item questionnaire. PTSD diagnostic status will be assessed using the past month version of the CAPS-5. The CAPS-5 has the advantages of categorical (diagnostic) or dimensional scoring of PTSD plus items for assessing social and occupational functioning, dissociation, and the validity of the items. A total severity score of 33 or higher indicates full threshold PTSD [7]. The CAPS-5 past week version quantitative data will be given prior to treatment and at follow-up (Visit 15) and used for evaluation of treatment (IASIS or sham) and for correlation with MEG data. PCL-5 [8] will also be given in Visits 1 and 15 to track changes in PTSD symptoms.

D.1.7. Alcohol, smoking, substance uses: We will utilize Alcohol, Smoking and Substance Involvement Screening Test (ASSIST) [15] to assess alcohol and substance use over the lifetime and frequency of past 3 months. Alcohol Use Disorders Identification Test (AUDIT) [16] will assess alcohol abuse problems.

D.1.8. Medications known to affect MEG: Participants will continue on their current medications. All medications taken by each participant will be noted during a pre-consent screening process, followed by another full screening during consent, in case of medication changes. Each medication is documented for its specific drug class and compared to the published information that documents the effects of specific drug(s) on EEG or MEG delta frequency band [66]. A small class of medications (e.g., some sedative neuroleptics) are known to increase EEG and MEG delta-band power [66]. The IASIS treatment will not interfere with the participant's ongoing treatment. If the participant is currently undergoing Cognitive Behavioral Therapy or Medication Treatment, they will still be enrolled in the study as this is an appropriate representation of the population. All participants will be allowed to be on their currently prescribed medications, but will be asked to remain on the same medication regimen during the course of the IASIS treatment. The participants enrolled must have been stable in their current medications for at least 6 weeks. Since we will focus on changes in MEG due to IASIS, allowing participants to remain on current medications should not affect the results.

D.1.9. Neuropsychological Exams will be performed to assess cognitive dysfunction and its correlation with abnormal MEG measures. Complete test batteries pre- and post-treatment will assess domains of cognition that have differentiated mTBI and HC in previous research [92,93] using measures previously validated for TBI [94]. These domains include verbal learning and retrospective memory (California Verbal Learning Test-2nd Edition) [92]; processing speed (Symbol Search and Coding subtests from the Wechsler Adult Intelligence Scale-4th Edition (WAIS-IV; [95])); executive function (Verbal Fluency, Trail-Making and Color- Word Interference subtests from the Delis-Kaplan Executive Function System [96]); and attention/working memory (WAIS-IV Digit Span subtest). Because preliminary analyses of our previous cohort showed that self reported symptoms of traumatic stress significantly correlated with impulsive responding on The Connors Continuous Performance Task II (CPT-II) [97], it will be included as a measure of attention and impulsivity. Impulsivity will also be measured by Barratt Impulsivity Scale [98], a self-report questionnaire. Since frontal lobe areas are more prone to damage, the Frontal Systems Behavior Scale [99] will measure behavioral dysfunction associated with frontal subcortical impairment. The Wechsler Test of Adult Reading [100] will provide an estimate of premorbid ability. Effort will be assessed using the Test of Memory Malingering (TOMM) [9]. Alternate forms of tests will be used post-treatment when available. As we require participants to adequately rate their symptoms during their treatment sessions, we would require that the symptom validity tests (SVT) measures be passed. If the participant fails the SVT measures, such as the TOMM, he/she will be removed from the study. In order to measure change at multiple time points, we will administer the Detection, Identification, and Two-back tests from CogState Ltd, a tablet-administered battery optimized with multiple versions for use in clinical trials. These will be administered pretreatment (Visit 1), at the treatment mid-point (Visit 9), and post-treatment (Visit 15).

D.2 Data Acquisition for MEG and MRI

MEG data acquisition: rs-MEG data will be measured in alert condition using our Elekta-Neuromag VectorView MEG system. The entire recording will have three 5-minute blocks with eyes closed and a 60 sec break with eyes-open between each block. The participant will be instructed to keep the eyes closed and empty his/her mind while staying alert (see [1]). Data will be sampled at 1000 Hz. Eye blinks, eye movements, and

heart signals will be monitored. Three minutes of empty-room data will also be acquired to assess the sensor and environment noises. Precautions are taken to ensure head stability and minimize head movements (< 3 mm) (see [1]). We focus on eyes-closed rs-MEG data since low-magnitude eye-related artifacts can be easily removed, whereas eyes-open rs-MEG data are often contaminated by eye-blanks and strong eye-movement artifacts that cannot be fully removed without substantially diminishing the brain signals.

Conventional MRI and the construction of the BEM: Using a 3T GE Discovery MR750 MRI scanner, we will acquire a high-resolution MRI volume with a resolution of 1 1 1 mm³ using a T1-weighted 3D-IRSPGR pulse sequence. Gradient nonlinearity spatial distortion in MRI will be corrected using software developed by our collaborator, [name] lab [22]. The T1-weighted images will be used to construct a source grid for Fast VESTAL and a boundary element method (BEM) model for MEG forward calculation [101]. BEM mesh is constructed by tessellating the inner skull surface from the T1-weighted MRI into ~6000 triangular elements with ~5 mm size. Cubic source grid with 5 mm size and ~10,000 nodes covering the whole brain is used to calculate the MEG gain (i.e., lead-field) matrix. Conventional MRI sequences for identifying mTBI lesions in Veterans will also be performed: 1) Oblique T2*-weighted; 2) Oblique T2-weighted with ASSET; 3) Oblique FLAIR; 4) Oblique DWI. Susceptibility-weighted imaging will also be performed to detect subtle blood products.

D.3 Detecting mTBI using Voxel-wise MEG Slow-wave Source Imaging and Conventional MRI (Aim 1)

D.3.1. MEG source imaging procedure for slow-waves: Eyes-closed rs-MEG data is first run through MaxFilter [102] to remove external interferences (e.g., artifacts due to metal objects, strong cardiac signals, environment noises, etc.), and to correct head movement. Next, residual artifacts due to micro eye-blanks, eye movements, and residual cardiac signals are removed using Independent Component Analysis using ICALAB (Riken, Japan). Here, the 2nd and 3rd 5-minute rs-MEG sensor-waveform datasets are registered to the 1st 5- minute dataset using MaxFilter. The artifact-free, eyes-closed, rs-MEG sensor-waveform datasets are divided into 2.5 second epochs. The data in each epoch are first DC-corrected and then run through a 1-4 Hz bandpass filter. Sensor-waveform covariance matrices are calculated for individual epochs after the band-pass filtering; then, the final sensor-waveform covariance matrix is obtained by averaging the covariance matrices across individual epochs for the total 15-minute data. Using such a covariance matrix, voxel-wise MEG slowwave source magnitude images are obtained for each participant following the Fast-VESTAL procedure [65].

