
injury or if it is a signature of ongoing neuronal rearrangement and healing that occurs at the site of the injury.

Specific Aim 1: To detect the loci of injury in Veterans with mTBI and assess the mechanisms underlying functional neuroimaging changes related to IASIS treatment, and for a subset of Veterans with remaining symptoms, additional Nexalin treatment, using rs-MEG slow-wave source imaging. Our voxel-wise rs-MEG source-imaging technique will be used to identify abnormal slow-wave generation (delta band) in the baseline and post-treatment MEG exams to assess treatment-related changes on a single-subject basis. Healthy control (HC) Veterans, matched for combat exposure, will be used to establish an MEG normative database. Test-retest reliability of MEG slow-wave source imaging for mTBI will also be examined.

Hypothesis 1: Veterans with mTBI will generate abnormal MEG slow-waves during the baseline MEG exam. Voxel-wise MEG slow-wave source imaging will show significantly higher sensitivity than conventional MRI in identifying the loci of injury on a single-subject basis. The test-retest reliability of MEG slow-wave source imaging is expected to be high, with intra-class correlation coefficient (ICC) ≥ 0.75 between two sequential MEG exams.

Hypothesis 2: In wakefulness, slow-wave generation is a signature of ongoing neural rearrangement/healing, rather than a negative consequence of neuronal injury. IASIS treatment will enhance neural rearrangement/healing by initially potentiating slow-wave generation immediately after each treatment session.

Hypothesis 3: IASIS will ultimately reduce abnormal MEG slow-wave generation in mTBI by the end of the treatment course, owing to the accomplishment of neural rearrangement / healing. In Veterans with mTBI who finish IASIS treatment, but not in the sham group, MEG source imaging will show a significant decrease in abnormal slow-waves at post-treatment exam. Such significant decreases will also be evident in both the voxel-wise and overall abnormal MEG slow-wave measures.

Specific Aim 2: To examine treatment-related changes in PCS and PTSD symptoms in Veterans with mTBI. PCS and PTSD symptoms will be assessed at the baseline and post-treatment follow-up visits.

Hypothesis 4: Compared with the sham group, mTBI Veterans in the IASIS treatment group will show significantly greater decreases in PCS symptoms between baseline and post-treatment assessments.

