Covariate variables to be included in above statistical analysis: Age, gender, education, combat exposure (DRRI-2), socioeconomics, OSU TBI-ID for lifetime history of TBI, ASSIST and AUDIT for alcohol and substance uses, and order of mTBI to PTSD will be added as covariates in the linear regression and ANOVA analyses in Sections D.4 - D.6. However, since these variables will be matched during our group assignment, we do not predict they will have major impact to the results of statistical analyses.

Exploratory studies: We will add 10 minutes rs-fMRI in Visit 2 to our existing MRI acquisition on a 3T system in the two mTBI groups, and use the data for exploratory FC analyses of the relationship between rsfMRI and rs-MEG using the approach described in [14]. We will also add an N-back MEG task in Visits 2 and 15 for exploratory analyses of changes in working memory function due to IASIS treatment. We have previously found that changes in rs-MEG neural patterns are highly associated with the working memory performance of the N-back MEG task [110].

D.8 Description and Justifications of Sampling Plan, Power Analysis, and Time Table

For assessing the specificity (1- false-positive rate) of the MEG slow-wave measures on a single-subject basis, the number of HC subjects in the normative database has to be sufficiently large. N=75 will allow us to reliably assess the normative datasets from HC participants. By choosing K=3 in the K-fold cross-validation approach, 2/3 (N=50) will be used to construct the normative database and the remaining 1/3 (N=25) to test the specificity, with reliable performance.

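### The reason given in D.1.8 for setting medication aside covers the change analyses (H2-H6) but not the baseline MEG detection rate in Hypothesis 1

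*Combined protocol and SAP*

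**What the plan says.** D.1.8 states that "A small class of medications (e.g., some sedative neuroleptics) are known to increase EEG and MEG delta-band power". It keeps medicated participants in the trial: "If the participant is currently undergoing Cognitive Behavioral Therapy or Medication Treatment, they will still be enrolled in the study". Each drug is recorded by class and compared with published effects on the delta band. Regimens must have been stable for 6 weeks, and participants are asked not to change them during treatment. The section then concludes: "Since we will focus on changes in MEG due to IASIS, allowing participants to remain on current medications should not affect the results". It does not say how the drug record will be used in any analysis.

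Hypothesis 1 (Section 6) makes two detection claims. The first is "Veterans with mTBI will generate abnormal MEG slow-waves during the baseline MEG exam". The second is "Voxel-wise MEG slow-wave source imaging will show significantly higher sensitivity than conventional MRI in identifying the loci of injury on a single-subject basis". A third part concerns test-retest reliability.

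D.3.2 to D.3.6 carry out the detection part. Delta-band source magnitudes are converted to Z-scores against healthy-control norms and the whole-brain maximum (Zcmax) is taken. The cut-off comes from Youden's index, with specificity of at least 90% for the MRI comparison. MEG and MRI sensitivity are then compared by McNemar's test. Under D.1.4, "HC subjects must not have been diagnosed with head injury, affective disorder, or PTSD".

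In D.7, a list of covariates that does not include medication "will be added as covariates in the linear regression and ANOVA analyses in Sections D.4 - D.6".

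**The concern.** The D.1.8 argument is a within-person one: if a stable drug raises delta equally before and after treatment, it cancels from the change. At a single baseline scan nothing cancels. A participant whose delta is raised by a drug has a higher Zcmax, and D.3.6 records a MEG-positive mTBI case whatever the cause.

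The bias has one direction. MRI is read for visible lesions, ventricular changes and hyperintensities, and nothing in the plan suggests that a delta-raising drug would alter that reading. Zcmax is a maximum over the brain, so a rise in any one region is enough.

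The resulting rate is a correct count of MEG positives in this sample. What is at stake is its reading as sensitivity to injury, because Hypothesis 1 speaks of finding the loci of injury and B.2 presents the method as an aid to diagnosis. B.2 also recognises that other conditions generate slow-waves and deals with them by exclusion, but does not mention drugs.

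**Working it through.** **Which analyses the D.1.8 argument covers**

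- H2 (D.4.3): before versus after a session. Change.
- H3 (D.4.4): Visit 2 versus Visit 15. Change.
- H4 and H5 (D.5): change in symptoms.
- H6 (D.6): correlation of changes.
- H1, detection part (D.3.5-D.3.6): baseline level against a norm. Not change.
- H1, reliability part (D.3.7): agreement between Visits 2 and 3. Not a detection claim.

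**Whether medication enters H1 elsewhere**

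- The normative model in D.3.2 names age, gender, combat exposure and education.
- D.7 applies to D.4-D.6 and omits medication.
- McNemar's test, as planned in D.3.6, has no covariates.

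No step uses the drug classes.

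**The plan's own figure**

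D.8 gives power above 0.98 for the McNemar comparison: odds ratio above 50, two-tailed alpha 0.01, N = 50 per mTBI group. The pilot rates in C.2 are 84.5% for MEG (71/84) and 7.1% for MRI (6/84). If MEG and MRI are assumed independent within a participant:

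- MEG positive, MRI negative: 0.845 × 0.929 = 0.785
- MEG negative, MRI positive: 0.155 × 0.071 = 0.011
- Odds ratio: about 71. Discordant share: 0.785 + 0.011 = 0.796.
- Exact McNemar power at N = 50: above 0.999.

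With the odds ratio held at 50, exact power is 0.988 once the discordant share reaches 0.35. The stated figure is reproduced.

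**Size of the inflation**

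Let s be the injury-related sensitivity. Let x be the share of mTBI participants whom a drug alone would push over the cut-off, taken as independent of whether their injury would be detected. Then

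observed = s + (1 − s)x, so s = (observed − x) / (1 − x).

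The documents give no value for x, so a range is shown. The observed rate is set at the pilot 84.5%.

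| x (assumed) | calculation | s | overstatement, points |
|---|---|---|---|
| 5% | 0.795 / 0.95 | 83.7% | 0.8 |
| 10% | 0.745 / 0.90 | 82.8% | 1.7 |
| 20% | 0.645 / 0.80 | 80.6% | 3.9 |
| 30% | 0.545 / 0.70 | 77.9% | 6.6 |
| 50% | 0.345 / 0.50 | 69.0% | 15.5 |

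Specificity has a matching limit. If controls take none of these drugs, 90% specificity in them becomes 0.90 × (1 − x) in uninjured people with the same exposure: 81.0% at x = 10% and 63.0% at x = 30%.

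**Does the McNemar conclusion move?**

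Using s in place of the observed rate, with MRI at 7.1%, N = 50 and alpha 0.01, exact power is still about 0.98 at x = 70% (s = 48.3%). It falls to 0.84 only at x = 75%. The test is robust at the pilot gap of 84.5 − 7.1 = 77.4 points; the point estimate is what shifts.

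**The case against.** The strongest reply is that the quoted sentence speaks only of change and makes no claim about H1, and that the stated primary goal is the neural basis of treatment-related change. That is fair as a reading of the sentence. But D.1.8 is the only place where the plan deals with drug effects on MEG, so H1 is left with no provision.

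Several stronger readings are tempting and should not be drawn.

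- **Delta-raising drugs are concentrated in the mTBI groups.** A reader might infer this from the control exclusions. D.1.8 covers all participants, sets no separate drug rule for controls and gives no usage rates. Its one example is some sedative neuroleptics, and schizophrenia and bipolar disorder are excluded in every group (D.1.2), which should limit their use.
- **PTSD or depression raises delta and is scored as injury.** Controls are free of both by design, and PTSD is matched only between the two mTBI arms. But the documents attribute a delta rise to drugs, not to PTSD or depression. These are possible confounders, undemonstrated here.
- **H1 is a test of mTBI against controls.** Its formal test is MEG against MRI, paired within mTBI participants. Controls supply the norm, the cut-off and the specificity.
- **The plan makes no provision at all.** D.1.2 promises to co-vary BDI-II in data analyses without limiting this to D.4-D.6, and the D.3.2 list of adjusted variables is open-ended. Neither mentions medication, and no D.3 step applies BDI-II.

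The objection that the inflation rests on assumed values also stands. So does the observation that the model is unfavourable to MEG, since everyone counted in x crosses the cut-off on the drug alone.

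**Conclusion.** The concern holds for medication and for the detection part of H1. The D.1.8 justification does not reach an analysis that scores a baseline delta level, and the recorded drug classes are not used there. The likely effect is an overstated MEG sensitivity: about 1.7 points at x = 10% and 6.6 points at x = 30%, given an observed 84.5%. Both values of x are assumptions, and the true share could be smaller.

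A reader might go further and doubt the superiority of MEG over MRI. The documents do not support that: at the pilot rates the McNemar result survives any plausible x. What needs care is the sensitivity figure, its attribution to injury, and the population in which specificity was measured. H2-H6 are not affected by this point. It is a modest point that can be settled from data the plan already records.

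**What to change.** 1. In D.1.8, limit the closing sentence to the change analyses (H2-H6).
2. In D.3.6, report MEG sensitivity, specificity and McNemar's test twice: for all participants, and without those on the delta-raising classes documented at screening. Fix the list of flagged classes before looking at Zcmax, and state whether the norm and cut-off are re-derived without flagged controls.
3. Add a table of drug use by class and group, including controls. This replaces the assumed x with an upper limit, the share exposed.
4. Describe specificity as measured in controls without PTSD or affective disorder. Detection rates by PTSD status (CAPS-5 of 33 or higher, the threshold in D.1.6) may be tabulated descriptively, labelled as a possible confounder.
5. Do not adjust Zcmax for CAPS-5 or BDI-II. D.3.2 fits its adjustments in controls, who have CAPS-5 below 8 and no affective disorder, so those data cannot support a coefficient for patients at much higher scores. Adjusting within the mTBI groups could remove injury signal, since the plan itself treats PTSD and later depression as possible consequences of the injury.

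The cost is small. Section 20 says study visits have stopped, and the fix needs only planned data; if it is added after H1 results are known, label it so. The restricted analysis is smaller. If 30% of the 100 mTBI participants were flagged (an assumption), 70 would remain, and the 95% half-width around 84.5% would grow from 1.96 × √(0.845 × 0.155 / 100) = 7.1 points to 1.96 × √(0.845 × 0.155 / 70) = 8.5 points. The sensitivity figure may also be less favourable. No enrolment or treatment rule changes.
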